9.3 Analysis Populations

All individuals enrolling in FUEL-OLE will be recruited for enrollment in the FALD study. At completion of FUEL-OLE, once FUEL assignments are unblinded (udenafil or placebo), the

cohort will be stratified into udenafil naïve vs. udenafil continuation groups. Analysis will be done both on an intent-to-treat and a per-protocol basis.

9.4 Statistical Analysis

9.4.1 General Methods

This is a prospective, observational, cohort study.

9.4.2 Primary Outcome

The absolute stiffness by SWE and by MR elastography will be reported using descriptive statistics as appropriate.

9.4.3 Secondary Outcomes

Secondary outcome 1

Baseline liver stiffness measured by ultrasound or MRI elastography will be compared between the two groups (U+ vs. U-) using appropriate statistics. Next we will assess change in liver stiffness from pre- to post-1 year udenafil treatment in the U-group as well as from 6 to 18 months of therapy in the U+ group.

Secondary outcome 2

Changes in liver stiffness, diastolic cardiac function (including E/E' and MPI), PAT measurement, and exercise measurements (including peak VO₂ and submaximal exercise measures) from baseline to 12 months will be quantified. Correlation between change in liver stiffness and changes in diastolic cardiac function and exercise measurements in the entire cohort and in the U- group and U+ group separately.

Secondary outcome 3

Bivariate analyses will examine 1) the correlation between each biomarker and liver stiffness measured by ultrasound and MRI elastography and 2) the correlation between change in each biomarker and change in liver stiffness from baseline to 12 months in both the U+ and U- cohorts.

The proteomic and transcriptomic data will be presented primarily as a descriptive report. Pairwise differences between groups may be sought using appropriate 2-group statistics, but we expect the limited sample size in this exploratory outcome to limit analysis to descriptive statistics.

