STATISTICAL ANALYSES	
Analysis Populations: All individuals enrolling in FUEL-OLE will be recruited for enrollment in the FALD study. At completion of FUEL-OLE, once FUEL assignments are unblended (udenafil or placebo), the cohort will be stratified into udenafil naïve vs. udenafil continuation groups. Analysis will be done both on an intent-to-treat and a per-protocol basis.
 
General Statistical Methods: This is prospective observational study of liver stiffness in Fontan patients. Absolute liver stiffness and association of degree of stiffness liver biomarkers will be assessed for the entire cohort. Change in liver stiffness over the 12-month FUEL-OLE duration will be assessed both for the overall cohort and after stratification into udenafil naïve vs. udenafil continuation groups.

FINAL DATE	December 11, 2017

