5.0 STUDY DESIGN

This is an open-label extension study that integrates with the FUEL Extension Trial. FUEL-enrolled patients will have been randomized and double-blinded to either placebo or udenafil, and all patients entering the FUEL Extension trial will be placed on udenafil therapy. Therefore, approximately 50% of patients eligible to be enrolled in our study will be udenafil-naïve (U-) and 50% will have already completed 6-months of therapy (U+). As a part of FUEL-OLE, each participant will receive one year of udenafil treatment (87.5 mg twice daily). Both the U- cohort and the U+ cohort will have liver stiffness measured by ultrasound and MR elastography (where available), as described above. Thus, the U- subjects will have elastography measurements pre-udenafil and after 1 year of treatment. This will determine the impact of udenafil therapy on liver stiffness. Additionally, the U+ cohort from FUEL will allow us to determine if potential benefits of udenafil therapy are sustained over time by comparing measurements after 6 (baseline entry into our study) and 18 months of therapy (after 1-year of our study). The study visits are as follows:

1. Baseline visit: during the baseline visit, subjects will undergo ultrasound SWE and, if available at their center, magnetic resonance elastography. These will be coordinated with FUEL extension testing to ensure that the primary study is not interrupted. The additional blood work for this protocol will be obtained at the same time as the blood work for the FUEL extension study.
2. Follow-up visit: during the follow-up visit, subjects will undergo ultrasound SWE and, if available at their center, magnetic resonance elastography. These will be coordinated with FUEL extension testing to ensure that the primary study is not interrupted. The additional blood work for this protocol will be obtained at the same time as the blood work for the FUEL extension study.

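### The whole-cohort correlations of stiffness with function change and with biomarker level carry no term for FUEL arm, so they can mix a between-arm drug difference with the within-arm association

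*Combined protocol and SAP*

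**What the plan says.** Three sets of correlations are planned in section 9.4.3.

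- **Outcome 2, change scores.** Change in stiffness is correlated with "changes in diastolic cardiac function and exercise measurements in the entire cohort and in the U- group and U+ group separately". There is therefore one pooled and two arm-specific versions.
- **Outcome 3, part 1, levels.** The plan examines "the correlation between each biomarker and liver stiffness measured by ultrasound and MRI elastography". No visit and no split by arm is given. The synopsis supplies the population: "Absolute liver stiffness and association of degree of stiffness liver biomarkers will be assessed for the entire cohort".
- **Outcome 3, part 2, change scores.** The plan examines "the correlation between change in each biomarker and change in liver stiffness from baseline to 12 months in both the U+ and U- cohorts". The natural reading is one correlation within each arm.

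No section adds arm as a covariate, plans a partial correlation, or says which version is the main one. Arm will be known: section 9.3 says that after FUEL is unblinded the "cohort will be stratified into udenafil naïve vs. udenafil continuation groups". Section 5.0 expects the two groups to be about equal. The U+ group enters after six months on drug and the U- group enters untreated. During the study year U- starts udenafil and U+ continues it.

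**The concern.** Arm is related to udenafil exposure at entry and to the change in treatment over the next 12 months. The protocol also gives reasons to expect udenafil to act on both sides of these correlations. Section 4.3 hypothesises lower stiffness through less venous congestion. Section 3.1.3 says the parent trial looks for better cardiac function, endothelial function and exercise performance. Section 3.2.2.3 names BNP and NT-proBNP as markers of congestion.

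If the arms differ in the mean of both measures, a pooled correlation is non-zero even when the two are unrelated within each arm. Under the protocol's own hypotheses the induced correlation would point the way that Secondary Aims 2 and 3 predict, so it could be read as support for them. Conversely, if the between-arm relation runs against the within-arm relation, the pooled figure understates a real association.

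**Working it through.** **The plan's own figure.** The documents give no sample size or power for any correlation. The only calculation (section 9.2) is for outcome 1: baseline mean 2.08 m/s, SD 0.24, a 10% reduction, alpha 0.05, 85% power, 12 per group. It reproduces with the paired normal formula: n = ((1.960 + 1.036) × 0.24 / 0.208)² = 11.95, so 12. This treats 0.24 as the SD of change.

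**Inputs for the correlation.**
- Share per arm p = 0.5 (section 5.0).
- Stiffness difference d1: 0.208 / 0.24 = 0.867 SD from the 10% effect, or 0.0375 × 2.08 / 0.24 = 0.325 SD from the 3.75% effect also named in section 9.2.
- Difference in the second measure d2: not in the documents; assumed, from 0 to 0.867 SD.
- N = 50 to 150 (section 6.1).

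**Formula.** With within-arm correlation ρ and differences in within-arm SDs,

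r = [ρ + p(1−p)d1d2] / √{[1 + p(1−p)d1²][1 + p(1−p)d2²]}.

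For ρ = 0, d1 = 0.867, d2 = 0.5: the numerator is 0.25 × 0.867 × 0.5 = 0.108, the denominator is √(1.188 × 1.0625) = 1.123, and r = 0.096.

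**False-positive rate** of the unadjusted whole-cohort test (ρ = 0, two-sided 5%, 20,000 simulated cohorts per setting):

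| d1 / d2 (SD) | induced r | N = 50 | N = 100 | N = 150 |
|---|---|---|---|---|
| 0.867 / 0.867 | 0.158 | 20% | 36% | 50% |
| 0.867 / 0.5 | 0.096 | 11% | 16% | 22% |
| 0.867 / 0.2 | 0.040 | 6% | 7% | 8% |
| 0.325 / 0.325 | 0.026 | 5% | 6% | 6% |
| 0.867 / 0 | 0 | 5% | 5% | 5% |

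The partial correlation given arm stays at 4.6% to 5.2% in every setting, with mean r about 0. The arm-specific correlations also hold about 5%.

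**Sensitivity to the SD of change.** The documents do not give it. If it is 0.24 × √(2(1 − c)), with an assumed baseline-to-12-month correlation c of 0.3 to 0.8, the 10% effect is 0.73 to 1.37 SD. The induced r is then 0.08 to 0.14 with d2 = 0.5 SD, and 0.12 to 0.32 with d2 = d1.

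**Masking.** With ρ = 0.3, d1 = 0.867 and an assumed opposing d2 = −1.0: (0.3 − 0.217) / √(1.188 × 1.25) = 0.07.

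**Precision of the alternatives** (Fisher z, true r = 0.3; SE 1/√(n−3), or 1/√(n−4) when adjusted):
- One arm of 25: 95% CI −0.11 to 0.62. Adjusted with all 50: 0.02 to 0.54.
- Power in one arm of 50: 56%. Adjusted with all 100: 86%, the same as unadjusted with all 100.

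**The case against.** The strongest reply is that the plan does use arm. Function change is correlated in each arm as well as pooled, and biomarker change is correlated by arm. These results are free of the artefact, so a pooled correlation that is absent within arms would be visible beside them. This stands. A reader might infer that the plan ignores FUEL arm throughout, and the text of 9.4.3 does not support that. Only the biomarker-level correlation has no arm version. Outcome 2 has no level correlation in 9.4.3 at all.

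A second reply concerns size. A reader might take 0.867 SD as a difference between arms that the protocol expects. It is not: section 9.2 states 10% as a before-after reduction within U-. To serve as an arm difference it needs no change in U+ (for change scores), or the full effect after six months (for baseline levels). The second measure's difference has no source in the documents. This also stands, and it makes the size conditional.

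Third, sections 9.4.2 and 9.4.3 set no significance test for the correlations, and section 9.1 leaves detail to a later SAP. The false-positive rates therefore apply only if a 5% test is used, but the bias in r does not depend on testing. A SAP still to be written is a reason to settle the matter there.

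Fourth, a shared drug response may be of interest in itself. Section 3.2.2.3 asks which biomarkers track stiffness change under udenafil. That is a reason to state the target, since an unadjusted coefficient cannot separate the two components.

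Lastly, arm-specific precision is not hopeless in larger cohorts: for r = 0.3, arms of 50 give 0.02 to 0.53 and arms of 75 give 0.08 to 0.49. They remain wider than an estimate that uses everyone.

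**Conclusion.** The point holds for two analyses: the pooled correlation of stiffness change with function change, and the biomarker-level correlation. The second is the more exposed because nothing by arm sits beside it. Its exposure is mainly at baseline, since all subjects are on udenafil by 12 months, and the plan does not name the visit.

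The artefact is material if the arms differ by roughly 0.5 SD or more in both measures (r about 0.10 to 0.16, false-positive rate 11% to 50% over N = 50 to 150). It is slight at 0.2 to 0.3 SD in one or both (5% to 8%), and absent if either measure does not differ by arm. These figures assume equal arms, no within-arm correlation and a two-sided 5% test. The documents do not show that a false finding is likely. They show that the pooled estimate is open to one, and that an inexpensive adjustment removes it. The change is worth making in secondary, associational analyses; it does not touch the descriptive primary outcome.

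**What to change.** In section 9.4.3, and in the SAP before database lock:

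1. State that the target is the association between stiffness and the other measure within FUEL arm.
2. Make the main whole-cohort estimate a partial correlation given FUEL arm, or a regression with an arm term. Apply it to outcome 2 change, to outcome 3 biomarker level with the visit named, and to outcome 3 biomarker change as a combined estimate.
3. Keep the U- and U+ correlations beside it, add them for biomarker level, and compare the arms with a Fisher z test as a heterogeneity check.
4. If the unadjusted correlation is shown, label it descriptive.
5. Align the synopsis sentence on biomarker association with this.

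The cost is wording, one degree of freedom, and the assumption of a common within-arm association, which item 3 examines (with limited power at these arm sizes). No further data are needed, because arm is available after unblinding.

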10.0 ETHICS AND GENERAL CLINICAL TRIAL CONDUCT CONSIDERATIONS

10.1 Institutional Review Board or Independent Ethics Committee

10.2 Ethical Conduct of the Clinical Trial, Confidentiality, and Potential Risks

The clinical studies in this proposal meet the criteria in the NIH Supplemental Instructions for Preparing the Human Subjects Section of the Research Plan for Scenario B: Non-exempt human subject research, non-clinical trial. Although this will be a study ancillary to a clinical trial, this study is not a clinical trial; it collects additional data and measurements on all patients regardless of their status within FUEL-OLE.

10.3 Potential Risks

Human Subjects Involvement, Characteristics, and Design

Young adults and pediatric patients with single ventricle congenital heart disease will be managed as per the parent FUEL-OLE trial and otherwise per the standard of care; laboratory, radiologic, and echocardiographic testing will be performed within the framework of the FUEL-OLE trial and at interim time points per the standard of care. The research team will not be involved in clinical decisions. Patient demographics and available clinical and laboratory data will be recorded for the purposes of research.

Biospecimen Collection

No additional venipuncture beyond that already being obtained in FUEL-OLE will occur. Minor temporary discomfort may be associated with the removal of blood by venipuncture. There is a risk of bruising and a very small amount of bleeding associated with the blood drawing. There is also a very small risk of infection at the site. Whenever possible, blood samples will be gathered when the participant is scheduled for routine blood testing or procedures. Serum collection will occur via venipuncture simultaneously with FUEL-OLE collection. The total amount of serum obtained for both studies will be 6mL (3mL for FUEL-OLE and 3mL for this study), which is within safe range for adolescent patients within FUEL-OLE's height and weight criteria. No DNA samples specific to FALD beyond what is already collected in FUEL-OLE will be obtained.

MRI

Risks related to MRI include subject distress/claustrophobia, projectile injury, and scanning with ferromagnetic implanted material (e.g., pacemaker or aneurysm clip) in the subject. Subjects experiencing distress/claustrophobia during MRI will be allowed to opt out of the MRI portion of the study; their US results will still be included in our results. Additionally, individuals with any

significant ferromagnetic objects, specifically implantable cardiac defibrillators or pacemakers, should not undergo MRI and will have US results included in the study. MRI scanners will be operated within U.S. Food and Drug Administration guidance to minimize energy imparted into the subject and tissue heating.

Ultrasound

There are no known risks to ultrasound SWE. FDA-approved US systems will be employed that operate within U.S. Food and Drug Administration guidance with respect to energy imparted into the patient (thermal index and mechanical index).

10.4 Protection against Risks

Investigators will take all reasonable measures to protect the confidentiality of subjects and their families, including the following:

Reporting of Test Findings

The results of future tests on biological specimens will not be released to the subject/family. There is a reasonable possibility that no findings will result from this research effort. If findings are detected, it may be years before any utility of these findings is realized. Further, if samples are “anonymized” prior to release to other investigators for research, it may not be possible to trace the results back to the subject.

If an incidental finding is found on a study clinical test such, the PI or other qualified member of the research team will take full responsibility for disclosing the findings to the patients/parents, communicating with their primary cardiologist with permission, or making appropriate cardiology referrals as indicated. The subject may choose to seek a second opinion and/or appropriate clinical care. This might change the subject's insurability and employability as it relates to the clinical finding only. The presumption is that detection of a potentially clinically significant finding will prove to be beneficial.

10.5 Potential Benefits

Study Findings

At the end of the study study results will be provided to treating/referring physicians (cardiologist, etc). If udenafil is shown to reduce liver stiffness, it is possible that this can modify progression of FALD and could directly benefit the enrollee. This may directly benefit an individual by attenuating the disease. It is possible that the liver scans obtained for the study will demonstrate significant abnormalities in liver stiffness, and they may also find areas of significant fibrosis or cirrhosis. Although the clinical significance of such findings remains

unclear to the field, appreciation of these individual findings is likely to be beneficial for an individual's care.

Biospecimens

Identification of optimal serum biomarkers of liver stiffness may directly benefit the individual by allowing serial monitoring of FALD. In addition, we hope that the proteomic and transcriptomic portion will help investigators to learn more about the relationship between genetic factors and pathophysiology of FALD. This information may help physicians provide better answers to families' questions regarding causes and risk. It may also provide clues to future interventions and/or treatments.

Indirect Benefit

There might be an indirect benefit from the awareness that study results may help to improve the care of children with similar problems in the future. Families may derive a sense of altruism, accomplishment, and contribution to furthering understanding of the problem through their participation.

10.6 Risk/Benefit Ratio and Importance of Information to be Obtained

The risk/benefit ratio is favorable for this study and adverse events are not anticipated. The baseline risk is minimal because there are no therapeutic interventions specifically for the FALD study. There are direct potential benefits as described above. In addition, although an individual subject may not benefit from participation, the results of this study will make important contributions to the improvement of knowledge of the causes of congenital heart disease (CHD), in the development of new diagnostic tests, and ultimately in the improvement of treatment and prognosis.

10.7 Study Limitations

While integrating with FUEL-OLE is a clear advantage and makes this FALD study feasible, the study will not have a placebo control arm. However, an active control (U+) should still allow assessment of how udenafil affects liver stiffness in a naïve patient. Each center may have access to only US SWE, MR elastography, or both. We expect most, if not all, centers to have access to US SWE, as it is now widely available, commonly employed in practice, and straightforward to use. Our (CCHMC) radiology core (including MRI physicist [name], and imaging post-processing laboratory) will be able to facilitate MR elastography capabilities at participating centers, ensuring the use of a standardized protocol across scanners. Experience in processing and analyzing/interpretation of this relatively new measurement technique should be mitigated by use of a radiology core. MR elastography is more difficult to add for currently non-capable centers, thus, MR elastography measurements will be limited to centers that have capabilities.

11.0 REGULATORY/ADMINISTRATIVE PROCEDURES AND DOCUMENTATION

11.1 Data Collection

Data for each SWE and magnetic resonance elastography will be generated from each site and recorded on a case report form. This form will serve as the source document for each test and will be used to enter data into an electronic data capture (EDC) system (eCOS). US SWE data will be recorded from each site. MREL data will need to be sent anonymized to CCHMC for central processing/analysis.

The biomarker core lab will generate results for each blood specimen and will transmit that data electronically into the EDC system (eCOS). Subject identification will follow the same system as for the FUEL Extension trial. Each imaging study will be associated with the FUEL Extension identification number and each blood sample will be labeled with that same number.

FUEL-OLE enrollment takes place over a 2 day period. For clarity, often the initial FUEL-OLE day (called hereafter OLE-D1) and the final day of FUEL are the same visit. This visit consists of informed consent and assent, blood sample collection, EndoPAT testing, an echocardiogram, and exercise testing. Based on experience with the Udenafil study, this day takes 5-6 hours in total. Subjects will then return the next day (OLE-D2) for drug administration and 6-minute walk. Subjects will return at 12 months of FUEL-OLE for a final day repeating the above tests. FALD will ideally be integrated into this schedule with keen attention to preserving the integrity of the FUEL-OLE parent trial and preventing study fatigue as detailed below for each step. This plan was vetted and approved by the FUEL study subcommittee.

Subject recruitment: FALD will only be recruited by either the site PI or a study coordinator after a commitment is given to participate in FUEL-OLE. Recruiting should be done at the same time point as OLE to prevent unnecessarily repetitive patient contact.

Consent/Accent: Consent and assent for FALD will be obtained immediately following but only after consent/assent for FUEL-OLE has been obtained.

Serum testing: Serum for the ancillary study will be obtained during the same venipuncture as used in FUEL-OLE. The serum sample will be processed, stored and shipped in parallel with the plasma sample that is being collected for the FUEL-OLE Trial. The processed serum (and the processed plasma for the FUEL-OLE protocol) will be shipped to the FALD core lab (University of Michigan) for testing. The ancillary study will require an additional 3 ml sample of blood (for a total of 6 ml).

Imaging: We have identified the morning of OLE-D2 as the optimal time for hepatic imaging.

[figure not shown]
Page 30 of 35

- US SWE: A complete US SWE exam lasts 5-10 minutes only. It is a portable test, and thus may be performed in either a radiology suite or any other clinical cardiology location used by the study. Additional limited anatomic imaging will also be obtained that takes approximately 1 minute.
- MRE: A complete MRE exam lasts approximately 15-20 minutes. Additional limited anatomic imaging will also be obtained that takes approximately 1 minute. Including patient travel to and from the MR scanner we anticipate an additional 20-40 minutes, making the total duration of MR testing 35-60 minutes.

All liver imaging should be able to be completed in 60-90 minutes.

- For initial FALD imaging, by starting OLE-D2 immediately with hepatic imaging at 7:30 or 8:00 AM, we would anticipate FUEL-OLE can begin its formal day's schedule with study drug administration by 9-9:30 AM. In total, we would expect OLE-D2 including hepatic imaging to still conclude by midday as anticipated by the FUEL-OLE protocol.
- For the OLE and FALD 12-month follow-up visit, we would again anticipate beginning the day for with hepatic imaging. To make this feasible, we can pay for hotel costs for those individuals enrolled in FALD at the 12-month visit so that the testing day may start early. Alternatively, imaging may be obtained at the end of the day following FUEL-OLE testing, although this is less ideal because exercise testing may influence FALD measures. Integration of same day testing should be feasible based on projected length of the testing day.

Imaging identifiers for these research studies will include only the site and subject study-specific ID. Following image obtainment at both time points, images from both US SWE and MRE will be sent to the imaging core. Images transferred will contain the site and subject identifiers and no protected health information.

